## **12.6 Laboratory Assessments**

Blood samples should be taken using standard venipuncture techniques. Blood sampling will be performed according to the site SOPs.

The following laboratory variables will be determined as outlined below:

The following routine clinical chemistry test will be performed at Screening: Fasting glucose, Uric acid, BUN (blood urea nitrogen), Creatinine, BUN/creatinine ratio, eGFR (estimated glomerular filtration rate), Sodium, Potassium, Chloride, Calcium, Albumin, HbA1C, Bilirubin, Alkaline phosphatase, AST (aspartate aminotransferase), ALT (alanine transaminase), CBC.

Patients will be asked to fast before all blood tests are done.

The total blood volume collected for clinical labs for the Screening visit will be approximately 5 ml of whole blood.

Any value outside the normal range will be flagged for the attention of the Investigator or designee at the site. The Investigator or designee will indicate whether or not the value is of clinical significance. If the result of the clinical chemistry test from the samples taken during the screening phase is indicated as clinically significant, the study subject will NOT be allowed into the study.

## **12.7 Biomarkers**

In addition to the blood drawn for the safety laboratory assessments, additional whole blood and serum samples will be collected for the biomarker analysis Day 1B (Baseline), Day 14 and Day 28.

Samples will be processed on site and stored in the - 80° C. Approximately 30 ml of whole blood will be drawn for biomarkers at each visit. Patients will be asked to fast for at least 8 hrs before blood for biomarkers is drawn.

Blood samples for Biomarkers will be taken at The following biomarkers will be evaluated:

1. Nitric Oxide metabolites and related biomarkers: nitrite, nitrate, total nitroso species, cyclic GMP
2. Panel of Redox-related Products/Messengers: sulfide, thiosulfate, sulfate; polysulfides, reduced and oxidised LMW thiols incl cysteine, HCys, GSH total antioxidant capacity (cu-based TAC), RedoxSys (electrochemical)
3. Acute phase proteins/stress markers: hsCRP, Cortisol
4. Pro-inflammatory cytokines/immune cell markers (Luminex): IL-1, IL-2, IL-4, IL-5, IL-6, IL-8, IL-10, IL-12, IL-13, IL-18, IFN1, TNFN

## **12.8 Sample Shipment**

All clinical chemistry samples are to be shipped overnight on dry ice to the central laboratory where samples will be analyzed.

All frozen serum and blood are to be shipped monthly on dry ice to the central laboratory. Shipments should be made only on Mondays and Tuesdays to ensure receipt of the specimens by Friday.

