8. Patients should fast for at least 8 hours before the test. Blood for clinical chemistry will be shipped to the central lab for processing
9. Blood samples for biomarkers will be collected and processed on site. Patients should fast for at least 8 hours before the test. Samples will then be frozen onsite and shipped on monthly bases to the Central lab for storage.
10. Blood for HbA1C only will be drawn at the Week 4A visit and shipped to central lab or processing.
11. Subjects will be counseled on the use of ABPM equipment
12. If subject undergoes ABPM procedures and equipment fails, subject will be scheduled for another ABPM session within 48 hours for Visit 1R or 4R.
13. AEs will be monitored throughout the trial
14. Soap and shampoo should be returned to the study coordinator

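### The protocol lists CBC under clinical chemistry and ships all clinical chemistry samples on dry ice, so as written the only scheduled CBC yields no valid result

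*Protocol*

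**What the plan says.** Protocol 12.6 introduces one list of tests with "The following routine clinical chemistry test will be performed at Screening". The list includes "Sodium, Potassium, Chloride, Calcium, Albumin, HbA1C" and ends with "AST (aspartate aminotransferase), ALT (alanine transaminase), CBC". On the specimen, the section says: "The total blood volume collected for clinical labs for the Screening visit will be approximately 5 ml of whole blood". It also makes these results an entry condition: a subject whose screening result is "indicated as clinically significant, the study subject will NOT be allowed into the study".

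Protocol 12.8 sets the transport rule for the group: "All clinical chemistry samples are to be shipped overnight on dry ice to the central laboratory where samples will be analyzed". Its next sentence deals separately with frozen serum and blood, which go monthly.

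Protocol Appendix A has a clinical chemistry row and no hematology row. Footnote 8 to that row says: "Blood for clinical chemistry will be shipped to the central lab for processing". SAP Table 1, footnote 1, repeats this. Footnote 9, on the biomarker row, differs: "Blood samples for biomarkers will be collected and processed on site", with freezing only afterwards. Footnote 10 limits the Week 4A chemistry draw to HbA1C.

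SAP Listing 16.2.8.1.1 expects white cells, red cells, hematocrit, hemoglobin, platelets and red-cell indices for each subject.

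**The concern.** A CBC is run on intact cells. Blood on dry ice freezes, and freezing and thawing break the cells open. This is general laboratory knowledge and rests on no source cited in the documents. A site that follows 12.6 and 12.8 to the letter would therefore freeze the CBC tube and make it unusable.

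Three things are at stake. Protocol 8.2 requires the screening evaluations to be finished and checked against eligibility before randomization on Day 1, and one of them could not be finished. The CBC would not be available for the clinical-significance judgment in 12.6. And because no later visit schedules a CBC, the hematology listings would have no valid cell counts from any scheduled visit.

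A second effect is possible. If whole blood is frozen before serum is separated, contents of the red cells enter the sample and raise analytes that are concentrated in those cells, potassium and AST among them.

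**Working it through.** The plan gives no figure to reproduce, so the check sets the sections side by side. One illustrative calculation follows.

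1. **Is CBC in the group that 12.8 governs?** Yes, on the text. 12.6 lists 17 items under the clinical chemistry heading, and CBC is the seventeenth. Appendix A offers no other row for it. The group is not confined to serum tests either: HbA1C, a whole-blood test, is in the same list, and footnote 10 attaches the Week 4A HbA1C draw to the clinical chemistry row.

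2. **Does 12.8 make an exception?** No. It covers all samples in the group. It is not simply a rule for aliquots already frozen, because the following sentence treats those as a separate monthly shipment.

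3. **Does the CBC result depend on whether serum is separated on site?** No. A CBC cannot be run on serum. If the tube is frozen, the counts are lost whatever is done with the chemistry tubes.

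4. **Does a later CBC replace it?** No. Appendix A marks clinical chemistry at Screening and Week 4A only, and footnote 10 restricts Week 4A to HbA1C. The Unscheduled Visit has no chemistry mark.

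5. **How many subjects?** Everyone screened. Protocol 15.1 plans 116 randomized, so at least 116, plus screen failures, whose number is not given.

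6. **Are potassium and AST affected?** Only if blood travels unseparated. Footnote 8 puts processing at the central laboratory and footnote 9 puts it on site for biomarkers, which points that way. But 12.8 describes the central laboratory's task as analysis, and footnote 8 may mean no more than that.

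7. **Size of the potassium effect under that condition.** The inputs are assumptions, not figures from the documents: hematocrit (Hct) 0.36 to 0.50, red-cell potassium 80 to 110 mmol/L, plasma potassium 3.5 to 5.0 mmol/L, complete lysis.

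   Measured K = Hct × red-cell K + (1 − Hct) × plasma K

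   - Low end: 0.36 × 80 + 0.64 × 3.5 = 28.8 + 2.24 = 31.0 mmol/L
   - Middle: 0.45 × 100 + 0.55 × 4.2 = 45.0 + 2.31 = 47.3 mmol/L
   - High end: 0.50 × 110 + 0.50 × 5.0 = 55.0 + 2.5 = 57.5 mmol/L

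   Across this range the value reflects cell contents and not the subject's plasma level. No comparable figure is given for AST.

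**The case against.** The strongest reply is that the documents elsewhere treat chemistry as a serum test and hematology as its own class. Protocol 15.3 names hematology and serum chemistry separately, SAP 3.2 gives serum chemistry as its example of laboratory values, and the SAP has separate hematology and chemistry listings. Read that way, 12.8 covers separated serum, for which dry ice is unremarkable, and the only fault is a loose list heading in 12.6. This does not rescue the CBC. The list and the schedule are what a site works from, both place CBC within clinical chemistry, and HbA1C in the same row shows that the term is not limited to serum. The reply does have force for potassium and AST, which is why that part is only conditional.

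Tube handling is also often set outside a protocol. The abbreviation list defines a Study Procedures Manual, Protocol 19.1 mentions procedures supplied by the sponsor, and 12.6 leaves blood sampling to site SOPs. Correct instructions may well exist there. None is cited for separation or shipping temperature, however, and one that differed would contradict 12.8, while Protocol 21 tells investigators to avoid deviations.

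A reader might infer that sites would exclude sound subjects or overlook real abnormalities. The documents do not support that. Under 12.6 the investigator or designee judges clinical significance, and a CBC without a result, or a potassium in the range above, would be recognized as a failed specimen. A redraw is the likelier outcome, although one shipped under 12.8 as written would fail in the same way.

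**Conclusion.** The point holds for the CBC: taken together, 12.6 and 12.8 give an instruction under which the trial's only scheduled CBC cannot produce a valid result, for every screened subject. This assumes that sites follow the text literally and that freezing destroys blood cells. For potassium and AST it holds only if footnote 8 means shipment of unseparated blood, and the potassium range of 31 to 57.5 mmol/L assumes complete lysis as well.

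A reader might go further and infer that the whole laboratory eligibility screen fails. The documents do not show this. The only numeric laboratory limit is creatinine (Protocol 7.3), and neither creatinine nor HbA1C is shown to become unusable. The blood pressure endpoint, the sample size and the efficacy analyses are not touched. This is an error in sample-handling wording that affects screening and safety laboratory data. It is worth correcting because the instruction is explicit and the remedy is small.

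**What to change.** - **Protocol 12.6:** list CBC under its own hematology heading, apart from the chemistry tests.
- **Protocol 12.8:** limit dry ice to samples that may be frozen, namely serum separated on site and biomarker aliquots. State that the CBC tube is shipped unfrozen under the central laboratory's stability conditions.
- **Protocol Appendix A footnote 8 and SAP Table 1 footnote 1:** reconcile both with 12.8, so that it is clear what is done on site and what at the central laboratory.

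The cost is a wording change, one unfrozen shipper for the CBC tube and a short on-site separation step for chemistry serum. Sites already process biomarker blood (Protocol 12.7), so the added burden is small.

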## 13 SAFETY ASSESSMENTS

Participants will report adverse events immediately to the Investigator and study personnel. A safety assessment will be performed at each visit. A manual or clinic BPx3 will be performed. Any patient with average systolic BP > 160 mmHg for two weeks or average systolic of > 170 mmHg at one visit should be discontinued and referred for further medical treatment. Likewise, any patient with average diastolic BP >100 for two weeks of readings or average diastolic BP > 105 mmHg reading at any one visit should be discontinued

### 13.1 Compliance

Participants will be asked to bring study medication with them to each scheduled visit. Study site will be provided with a scale and weight of the study medication will be obtained before the first use and at each visit.

### 13.2 Pregnancy Reporting

Any pregnancy will be reported by study participants during their study participation. Participants who report pregnancy or lactation during the review of inclusion/exclusion criteria prior to randomization will not be enrolled in the trial. In case of pregnancy, Investigational Product should be discontinued and the Sponsor informed. Follow-up of the pregnancy will be mandatory until the outcome is available.

### 13.3 Study Completion

A completed participant is one who has completed all study visits. Day 42 study visit is defined as the participant's last visit.

## 14 EFFICACY ASSESSMENTS

For each patient and for each treatment Period, two values of Systolic and Diastolic Blood Pressure respectively (average value on active: average value on vehicle) will be calculated and then the difference between the two will be compared so that each patient has a single treatment response.

## 15 STATISTICAL CONSIDERATIONS

### 15.1 Sample Size

A total sample size of 116 randomized subjects, stratified into 2 cohorts (4 pumps or 8 pumps of study drug) of 58 subjects each allows for a dropout rate of 10%. It is expected that each strata will have at least 52 subjects with sufficient data needed determine the effect of the investigational product on blood pressure.

With the planned number 52 subjects per arm, the study is powered 80%, to detect a treatment effect = 5.8, SD = 11 (higher SD than was observed in Phase 1b/2a) ,with alpha = 0.05.

Based on the above sample size, the study is powered 90% to detect the treatment effect of 5.8 and SD = 9, that were observed in the Phase 1b/2a study.

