3. GENERAL STATISTICAL METHODS

3.1. Sample Size Justification

A total sample size of 116 randomized subjects, divided into 2 arms (placebo or B244) of 58 subjects each allows for a dropout rate of 10%. It is expected that each strata will have at least 52 subjects with sufficient data needed determine the effect of the IP on blood pressure.

With the planned number 52 subjects per arm, the study is powered 80%, to detect a treatment effect = 5.8 (mean change in systolic blood pressure from baseline), standard deviation (SD) = 10.5 (higher SD than was observed in Phase 1b/2a), with alpha = 0.05, using a 2-sample t-test.

Based on the above sample size, the study is powered 90% to detect the treatment effect of 5.8 (mean change in systolic blood pressure from baseline) and SD = 9, using a 2-sample t-test, that was observed in the Phase 1b/2a study.

In the planned analyses, mixed models will be used to account for the correlation of the assessments over time and provide a more robust analysis of the endpoint.

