Tabulations will be produced for appropriate demographic, baseline, efficacy, and safety parameters. For categorical variables, summary tabulations of the number and percentage of subjects within each category (with a category for missing data) of the parameter will be presented. For continuous variables, the number of subjects, mean, median, SD, minimum, and maximum values will be presented.

Formal statistical hypothesis testing will be performed on the primary and secondary efficacy endpoints with all tests conducted at the 2-sided, 0.05 level of significance. Comparisons of baseline characteristics will be performed in order to assess comparability of the treatment arms. Summary statistics will be presented, as well as 2-sided 95% CIs on selected parameters, as described in the sections below. P-values will be rounded to 4 decimal places. P-values that round to 0.0000 will be presented as <0.0001 and p-values that round to 1.00 will be presented as >0.9999.

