5. CHANGES TO PLANNED ANALYSES

The following changes between the study protocol are described below.

Editorial edits have been made in [Section 1.1.1](#) (Introduction), [Section 1.2.1](#) (Synopsis of Study Design), [Section 1.2.2](#) (Randomization Methodology), and [Section 1.2.5](#) (Efficacy Parameters) to clarify the information from the study protocol.

The schedule of events was changed according to an administrative letter from AOBiome dated 08 February 2017. Subjects were instructed to continue use of IP through end of the ABPM monitoring period (Day 29 [Visit 4B] and to weigh the IP after this visit. Subjects who had already completed the Day 29 visit prior to the notification should have used the IP through Day 28 and weighed the product on this visit.

The SD in the sample size was changed from 11 to 10.5 in order to estimate power correctly.

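### Power at the protocol's planning SD of 11 is about 76%, not the stated 80%; the SAP moves the SD to 10.5, where 80% holds, without giving the power at 11 or a source for 10.5

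*Protocol*

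**What the plan says.** Protocol 15.1 plans 116 randomised subjects in two groups of 58 and expects 52 in each after 10% dropout. It then states: "With the planned number 52 subjects per arm", "the study is powered 80%, to detect a treatment effect = 5.8, SD = 11", "with alpha = 0.05". It describes the SD of 11 only as larger than the Phase 1b/2a value. A second statement gives 90% power for the same effect at SD 9, which it attributes to Phase 1b/2a. The protocol names neither the test nor the sidedness.

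SAP 3.1 defines the groups as "divided into 2 arms (placebo or B244) of 58 subjects each allows for a dropout rate of 10"%, keeps 52 per arm, 5.8 mmHg and 80%, and gives "standard deviation (SD) = 10.5 (higher SD than was observed in Phase 1b/2a"), "with alpha = 0.05, using a 2-sample t-test". It repeats 90% at SD 9. SAP 3.2 sets "all tests conducted at the 2-sided, 0.05 level of significance".

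SAP Section 5 records the change: "The SD in the sample size was changed from 11 to 10.5 in order to estimate power correctly".

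**The concern.** The two documents claim the same 80% power for the same sample size and effect at two different SDs. Both cannot be right under one method.

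An SD is an assumption about patients, and power follows from it. When a power figure is found to be wrong for its inputs, the direct correction is to restate the power. Here the SD was restated instead, with no variance data cited, and the power at the protocol's less favourable SD was left unreported.

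What is at stake is how the result is read, above all a non-significant one. A reader who takes 80% at SD 11 from the protocol will believe that the type II error in that scenario is 20%, when it is about 24%.

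**Working it through.** **Inputs.** n = 52 per arm and effect d = 5.8 mmHg (Protocol 15.1, SAP 3.1); SD = 11 (Protocol 15.1), 10.5 (SAP 3.1) and 9 (both); alpha = 0.05 (both), two-sided (SAP 3.2); two-sample t-test of B244 against placebo, 1:1 (SAP 3.1).

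**Formula.** Standard error SE = SD × √(2/n); noncentrality δ = d/SE; degrees of freedom 2n − 2 = 102; critical value t = 1.9835. Power is the probability that a noncentral t variable with 102 degrees of freedom and noncentrality δ falls outside ±1.9835.

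**Step 1: check the method on the figure that both documents share (SD 9).** SE = 9 × √(2/52) = 1.765; δ = 5.8/1.765 = 3.286; power 90.2%. The stated 90% reproduces.

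**Step 2: the same method at the other two SDs.**

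| SD | SE | δ | Power (t) | Power (normal approx.) | Stated |
|---|---|---|---|---|---|
| 9 | 1.765 | 3.286 | 90.2% | 90.8% | 90% (both documents) |
| 10.5 | 2.059 | 2.817 | 79.7% | 80.4% | 80% (SAP) |
| 11 | 2.157 | 2.689 | 75.9% | 76.7% | 80% (protocol) |

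The SAP's pair of figures reproduces. The protocol's 80% at SD 11 does not.

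**Step 3: can another reading rescue the protocol's figure?**

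| Reading, t-test | SD 11 (stated 80%) | SD 9 (stated 90%) |
|---|---|---|
| 52 per arm, two-sided | 75.9% | 90.2% |
| 52 per arm, one-sided | 84.8% | 94.7% |
| 58 per arm, two-sided | 80.4% | 93.1% |

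Using all 58 randomised per arm would return 80% at SD 11, but the sentence says 52, and the companion figure would then be 93%. None of these readings gives both protocol figures.

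**Step 4: what SD 11 and 80% would imply.** Solving for the effect at n = 52 gives 6.10 mmHg. Solving for n at 5.8 mmHg gives 58 evaluable per arm; with 10% dropout, 58/0.90 = 64.4, so 65 randomised per arm and 130 in total.

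**Step 5: where 10.5 lies.** The SD that gives exactly 80% with 52 per arm and 5.8 mmHg is 10.46 (t) or 10.56 (normal approximation). The SAP's 10.5 lies between the two.

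**The case against.** A reader might infer that the SAP hid the shortfall, or that its SD was fitted to the target. The documents do not support the first and do not establish the second. SAP Section 5 prints the old value, the new value and the reason, so anyone who reads it learns that 80% did not hold at SD 11; only the size of the gap is missing. That 10.5 sits almost on the 80% solution, and that the reason given concerns power, makes fitting a plausible explanation, but the text says nothing about how the value was chosen.

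Nor is 11 better founded than 10.5. Each is justified only as exceeding the Phase 1b/2a value, and 9 is the only SD attributed to data. The trial cannot be held to 11 as the right SD.

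The t-test is also only a planning proxy. SAP 4.3.1 puts baseline blood pressure in the primary model. If baseline explains part of the variation in change, the residual SD falls to SD × √(1 − r²). The documents give no r. As an assumption, r = 0.2, 0.31 and 0.4 would give about 77.6%, 80.0% and 82.8% at SD 11, ignoring small losses of degrees of freedom. The primary population is ITT (SAP 2.1) and the mixed model uses partly observed subjects (SAP 3.10), so more than 52 per arm may contribute; 55 per arm would give 78.2%. This tells against saying that the trial is underpowered for its purpose. It does not make the protocol sentence correct, because SAP 3.1 rests its power claim on the t-test with 52 per arm.

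Lastly, Protocol 15.1 describes the groups of 58 as the 4-pump and 8-pump cohorts, and only the SAP defines them as B244 and placebo. The check follows the SAP.

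**Conclusion.** The point holds as a correction to a stated figure. Under a two-sided 0.05 two-sample t-test with 52 per arm, B244 against placebo, power for 5.8 mmHg at SD 11 is 75.9%, about 4 points below the stated 80%. The SAP's figures at SD 10.5 and SD 9 are correct to rounding. What remains is an uncorrected protocol sentence, an SD of 10.5 with no cited source, and no statement anywhere of the power at SD 11.

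The result rests on the SAP's test, sidedness and definition of the arms, which the protocol does not give. The protocol's own 90% at SD 9 agrees with the two-sided test at 52 per arm. The error does not invalidate the design or the planned analysis.

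**What to change.** - **SAP 3.1:** report power for 5.8 mmHg with 52 per arm, two-sided 0.05 t-test, as about 90% at SD 9, 80% at SD 10.5 and 76% at SD 11. If 10.5 has a source, cite it; otherwise call it a planning assumption.
- **SAP Section 5:** state that the protocol's 80% at SD 11 was a miscalculation and that the correct value is about 76% (80% at SD 11 corresponds to 6.1 mmHg).
- **Protocol 15.1:** correct the sentence to match at any next amendment. It does not justify an amendment of its own: under Protocol Section 28 that needs ethics approval, and the SAP (19 June 2017) falls in the month planned for database lock.

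The cost is a sentence or two in each place and a slightly less favourable stated power. Sample size, allocation and analysis stay as they are.

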## **15.2 Populations for Analysis**

ITT: includes all randomized participants.

Safety: includes all subjects who received at least 1 dose of study medication.

Per Protocol: subjects who administered at least 50 % of IP , have at least one baseline and post baseline in clinic systolic blood pressure measurement , and did not have any major protocol violations.

